5.3. Lifestyle Considerations

Not applicable.

5.4. Screen Failures

Screen failures are defined as patients who consent to participate in the clinical trial but are not subsequently randomized. A minimal set of screen failure information is required to ensure transparent reporting of screen failure patients to meet the Consolidated Standards of Reporting Trials publishing requirements and to respond to queries from regulatory authorities. Minimal information includes demographics, reason for screen failure, eligibility criteria, and any serious adverse events (SAEs) related to study-related procedures.

The screening eligibility period is 21 days as defined in [Section 4.1](#). An individual who does not meet the criteria for participation in this trial is referred to as a screen failure.

5.4.1. Rescreening

Patients may be rescreened one time after initial screening for any of the following reasons:

- ALSFRS-R value at original screening > 44. To be eligible, a patient's ALSFRS-R total score at rescreening must be ≤ 44 OR there is a drop in the score of 2 or more points compared to their original screening score. Rescreening for this reason must be done 60 days (± 7 days) after initial screening
- Not on stable edaravone or riluzole doses at original screening. To be eligible, if taking riluzole, must be on riluzole for 30 days prior to rescreening or not taking it for 30 days prior to rescreening; if taking edaravone, must have completed at least 2 cycles of edaravone at the time of rescreening or not received it for at least 30 days prior to rescreening. If taking the combination product (brand name only) of sodium phenylbutyrate and taurursodiol, must be on it for ≥ 51 days prior to rescreening or not

have taken it for at least 30 days prior to rescreening. Rescreening may occur once the necessary time interval has passed.

- Poorly controlled systemic hypertension at original screening. Rescreening may occur once the hypertension is adequately controlled
- Received an investigational device or drug or a prohibited drug as described in [Section 5.2](#), Item 209, within 30 days (or less than 5 half-lives, whichever is longer), at original screening. Rescreening may occur once the necessary time interval has passed.
- Was outside the screening window for their original Day 1 visit. Rescreening may occur once scheduling permits both rescreen and Day 1 visits to occur within the 21-day window

Patients must re-sign an informed consent before they are rescreened. At rescreening, they must meet all inclusion/exclusion criteria at the time of rescreening and have all elements of the screening visit performed again to be eligible. Patients may only rescreen once.

If an element of the screening visit could not be performed for logistical reasons (eg, trained evaluator was out sick, lab kits or outcome measure device was unavailable) the patient can return within the screening eligibility period to complete the visit.

Retesting for abnormal lab work within the original screening period may also be performed if there is reason to believe the repeat labs may improve and not be clinically significant and the patient is otherwise eligible to participate. Patients cannot be retested for abnormal bilirubin laboratory results. Patients who are retested for abnormal laboratory results during the original screening eligibility period do not need to re-sign an informed consent.

No waivers will be granted regarding inclusion/exclusion criteria.

6. INVESTIGATIONAL PRODUCT

This section describes any study drug: investigational product (IP) (ie, reldesemtiv) or placebo intended to be administered to a trial patient according to the protocol.

6.1. Study Drug Administered

Table 2: Study Drug

Arm Name	Active	Placebo
IP/Product Name	Reldesemtiv	Placebo
Type	Drug	Drug
Dose Formulation	Tablet	Tablet
Unit Dose Strength(s)	150 mg	Matching placebo
Dosage Level(s)	2 tablets twice a day for 600 mg TDD	2 matching placebo tablets twice a day
Route of Administration	Oral or via gastrostomy tube	Oral or via gastrostomy tube
Use	Experimental	Placebo
IMP	IMP	IMP
Sourcing	Patheon, Inc. Toronto Regional Operations (TRO) [name]	Patheon, Inc. Toronto Regional Operations (TRO) [name]
Packaging and Labeling	IP will be provided in bottles. Each bottle will be labeled as required per country requirement	Placebo will be provided in bottles. Each bottle will be labeled as required per country requirement
Excipients in Active and Placebo tablets	Microcrystalline cellulose Croscarmellose sodium Sodium lauryl sulfate	Lactose monohydrate Providone Magnesium stearate

IMP = investigational medicinal product; NIMP = non-investigational medicinal product

6.2. Preparation/Handling/Storage/Accountability

The investigator or designee must confirm appropriate temperature conditions have been maintained during transit for all IP received and any discrepancies are reported and resolved before use of the IP.

Only patients randomized in the trial may receive study drug and only authorized site staff may supply or administer study drug. All study drug must be stored in a secure, environmentally controlled, and monitored (manual or automated) area in accordance with the labeled storage conditions with access limited to the investigator and authorized site staff. Study drug may be shipped to patients by the site to avoid drug interruption.

The investigator, institution, or the head of the medical institution (where applicable) is responsible for study drug accountability, chain of custody, reconciliation, and record maintenance (ie, receipt, reconciliation, and final disposition records).

Further guidance and information for the final disposition of unused study drug are provided in the Pharmacy Manual.

IP should be stored at or below 25°C.

6.3. Measures to Minimize Bias: Randomization and Blinding

All patients will be centrally assigned to randomized study drug using an Interactive Web Response System (IWRS). Before the trial is initiated, the log in information & directions for the IWRS will be provided to each site.

Study drug will be dispensed at the study visits summarized in the SoA ([Section 1.3](#)). Returned study drug should not be re-dispensed to the patients.

The IWRS will be programmed with blind-breaking instructions and the unblinding procedure is documented in the IWRS User Manual. In case of an emergency, the investigator has the sole responsibility for determining if unblinding of a patient's treatment assignment is warranted. Patient safety must always be the first consideration in making such a determination. If the investigator decides that unblinding is warranted, the investigator should make every effort to contact Cytokinetics prior to unblinding a patient's treatment assignment unless this could delay emergency treatment of the patient. If a patient's treatment assignment is unblinded, Cytokinetics must be notified within 24 hours after breaking the blind. The date and reason that the blind was broken must be recorded in the source documentation and CRF, as applicable.

An unblinded physician (unmasked to renal labs but blinded to treatment assignments) who is not on the study team may direct a study drug interruption and a down-titration of patients based upon review of unmasked renal function laboratory values that meet the prespecified criteria ([Section 6.6](#) and [Section 7.3](#)). In order to preserve blinding of site staff and the study operation team, a small number of placebo patients will be selected for dummy down-titration during the study by the unblinded Clinical Research Organization (CRO) physician and will undergo repeat laboratory testing similar to what could be directed for patients receiving active treatment with laboratory abnormalities. The blinded down-titration selection criteria and records will be documented by the unblinded physician and the unblinded statistician separately. In order to maintain the blind, placebo patients who had a dummy down-titration during the double-blind dosing period will take 150 mg bid of reldesemtiv during the active drug period.

The randomization treatment assignments for individual patients will remain blinded to site staff and patients until the entire study is completed and the database is locked.

6.4. Study Drug Compliance

When patients are dosed at the site, the route, the date and time of the dose administered in the clinic will be recorded in the source documents and recorded in the CRF.

When patients self-administer study drug at home, compliance with study drug will be assessed at each visit. Compliance will be assessed by counting returned tablets during the in-clinic visits,

through documentation in the patient's dosing diary, the source documents and the CRF. Deviation(s) from the prescribed dosage regimen should be recorded in the CRF.

All study drug should be taken either with food or within 2 hours following eating food. Water may be consumed ad libitum.

- During the study, patients who lose the ability to swallow tablets can continue in the study taking crushed tablets. The crushed tablet dose can be administered either as: Crushed tablets in approximately 30 mL (2 tablespoons) of applesauce (or a vehicle of similar consistency) administered orally, followed by up to 250 ml (one cup) of water
- Crushed tablets suspended in approximately 3 tablespoons of water administered through a PEG tube, preceded and followed by 118 mL (1/2 cup) of water to flush the tube

A record of the number of study drug tablets dispensed to and taken by each patient must be maintained and reconciled with study drug and compliance records. Study drug dosing start and stop dates, including dates for dosing delays and/or dose reductions, and date of route change, will also be recorded in the CRF.

6.5. Concomitant Therapy

Any medication, including over-the-counter or prescription medicines, vitamins, and/or herbal supplements, that the patient is receiving at the time of enrollment or receives during the trial must be recorded along with:

- Reason for use
- Dates of administration including start and end dates
- Dosage information including dose, frequency and route of administration

The Medical Monitor should be contacted if there are any questions regarding concomitant or prior therapy.

Patients may continue to take prescription medications and non-prescription medications which in the opinion of the investigator and the Medical Monitor, will not interfere with the trial.

During the trial, medications and doses should remain stable whenever appropriate. However, investigators may prescribe or adjust any concomitant medication or treatment deemed necessary to provide adequate supportive care.

Prior use of riluzole, edaravone and the combination product (brand name only) of sodium phenylbutyrate and taurursodiol, even if stopped prior to screening, will be recorded along with the reason why it was stopped (patient choice, adverse event, cost). Patients should neither stop nor start edaravone, riluzole or the combination product of sodium phenylbutyrate and taurursodiol following randomization. However, it is recognized that changes in medications may occur including those due to the development of adverse events potentially related to these medications or changes in insurance coverage. Patients who start or stop edaravone, riluzole and the combination product (brand name only) of sodium phenylbutyrate and taurursodiol following randomization will be permitted to continue in the trial.

Drug-Drug Interactions

Medications that strongly inhibit the activity of CYP3A4 should be avoided from 7 days before the start of dosing (Day 1) through the last day of dosing (Week 48). Medications that strongly induced the activity of CYP3A4 should be avoided from 14 days before the start of dosing (Day 1) through the last day of dosing (Week 48). Please refer to Appendix 4 ([Section 10.4](#)) for the most common strong inhibitors and inducers of CYP3A4. Medications that are OCT1/OCT2 substrates should be avoided from 7 days before the start of dosing or used with caution during the trial, as reldesemtiv may have the potential to inhibit OCT1 and OCT2-mediated transport. Please refer to Appendix 4 ([Section 10.4](#)) for the most common OCT1/OCT2 substrates that should be avoided or used with caution.

6.6. Dose Modification

Any dose interruption, as described in [Section 7.1](#) must be documented in the CRF and include the reason for stopping, the stop date, and the restart date. For study drug dose management in relation to renal or hepatic abnormal laboratory values, see [Section 7.3](#) and [Section 7.4](#).

Following a dose interruption for adverse events other than those related to renal labs, if the adverse event is thought to be potentially related to study drug, the investigator may restart the study drug when symptom(s) have resolved or have substantially improved, and there are no safety concerns before resuming the study drug. If the patient has been off study drug for more than 7 days, the investigator may choose to see the patient in the clinic or via telemedicine prior to resuming study drug. While investigators are encouraged to resume dosing at 2 tablets twice a day, down-titration of the dose to 1 tablet twice a day is an option. If the patient resumed the study drug at 2 tablets twice a day and has recurrence of the AE, the investigator once again should have the patient temporarily interrupt dosing until the symptom(s) have resolved or have substantially improved, and there are no safety concerns before resuming the study drug. If the study drug is resumed, the patient should be down-titrated to 1 tablet twice a day.

Once down-titration occurs for any reason, no subsequent up-titration to the prior dose should occur.

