Patients must interrupt study drug for certain specified laboratory abnormalities. Hepatic related interruptions are permanent discontinuations. For renal related laboratory abnormalities, the interruption continues until the laboratory value in question has returned to the threshold specified in the protocol for re-initiation of treatment. Patients may then resume dosing at 1 table twice a day thereafter (150 mg twice daily). Patients also may be down-titrated to 1 tablet twice a day by the Investigator in the case of adverse events felt to be related to study drug. Once patients have been down-titrated to one tablet twice daily for any reason, their dose may not be returned to two tablets twice daily.

Data Monitoring Committee:

An independent Data Monitoring Committee (DMC) will periodically assess patient safety in an unblinded manner during the course of the trial.

Interim Analyses:

Twelve (12) weeks after approximately one-third or more of the planned sample size is randomized, the first interim analysis may be triggered. Its purpose is to determine if there is a lack of effect of reldesemtiv on the ALSFRS-R in CY 5031, a finding that would be inconsistent with the prior observed effect on the change from baseline at 12 weeks in ALSFRS-R total score in the Phase 2 trial, CY 5022. At this interim analysis, the DMC will receive unblinded efficacy data from the independent, third-party biostatistical group supporting them and assess the effect of reldesemtiv on the change from baseline to Week 12 in the ALSFRS-R total score. At this interim assessment, if the treatment difference for change from baseline to Week 12 in ALSFRS-R total score has a one-sided p-value larger than or equal to 0.5 (ie, the estimated treatment difference of the change from baseline at Week 12 in ALSFRS-R total score is favoring placebo), the DMC may recommend stopping the trial due to futility. This futility analysis based on the data of change from baseline to Week 12 in ALSFRS-R will not have any alpha spending in the final analysis of the trial. The Sponsor will monitor the blinded aggregate standard deviation of the change from baseline to Week 12 in ALSFRS-R total score periodically and possibly adjust the specified p-value before this interim analysis is conducted.

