4.3. Justification for Dose

The principle for dose selection is to ensure the potential benefits outweigh the risks of treatment with reldesemtiv, based on data from the dose ranging trial of CY 5022. In the Full Analysis Set (FAS), all three reldesemtiv dose levels appeared to be pharmacodynamically active. The totality of data in CY 5022 suggested that the three reldesemtiv dose levels had similar effects on ALSFRS-R and SVC; however, the more complete experience in the reldesemtiv clinical development program (as well as the clinical experience with tirasemtiv, another fast skeletal muscle troponin activator with a mechanism of action identical to that of reldesemtiv) indicates that higher exposures are associated with greater increases relative to placebo in skeletal muscle force production. Consequently, there is a rationale for using the highest dose of reldesemtiv that is safe and well tolerated in CY 5031.

The 450 mg dose level was associated with a higher rate of AEs related to nausea, decline in eGFR, elevations in ALT and AST and early terminations (compared to the 300 mg and 150 mg dose levels) in CY 5022. The dose selected for CY 5031 is 300 mg bid based on better tolerability compared to 450 mg bid with relatively similar efficacy between the two doses. A down titration to one tablet bid (for those assigned reldesemtiv, the dose would then be 150 mg bid) may be implemented for patients who experience an adverse event (AE) that is believed to be study drug related. See [Section 6.6](#) for details regarding dose modification. Since elevations in transaminases and declines in eGFR_{CysC} were dose related, by resuming drug at a lower dose for the remainder of the trial, the reoccurrence of the lab abnormality is expected to be less likely to occur.

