7.4. Liver Function Monitoring and Study Drug Management

ALT, AST, alkaline phosphatase (ALP) and total, direct, and indirect bilirubin will be obtained in accordance with the schedule of events.

Patients with abnormal hepatic laboratory values [ie, ALP, AST, ALT, total bilirubin (TBL)] or signs/symptoms of hepatitis should be evaluated to determine if the criteria for permanent discontinuation of study drug have been met. Patients who meet the criteria for permanent discontinuation must not be re-challenged. If a PI decides to hold study drug for abnormal lab values that don't meet the mandated threshold, this is also considered a permanent discontinuation and the patient must not be re-challenged.

Criteria for permanent discontinuation of study drug due to potential hepatotoxicity

- Elevation of either AST or ALT according to the following schedule:

Baseline AST or ALT Value	AST or ALT Elevation
Any	>8 × ULN at any time
Any	>5 × ULN but <8 × ULN for ≥2 weeks
Any	>5 × ULN but <8 × ULN and unable to adhere to enhanced monitoring schedule
Any	>3 × ULN with clinical signs or symptoms that are consistent with hepatitis (such as right upper quadrant pain/tenderness, fever, nausea, vomiting, jaundice)

OR

- TBL $>3 \times$ ULN at any time

Study drug **must** be also discontinued permanently if ALL of the criteria below are met:

- TBL $>2 \times$ ULN or international normalized ratio (INR) >1.5

AND

- increased AST or ALT from the relevant baseline value as specified below:

Baseline AST or ALT Value	AST or ALT Elevation
$<ULN$	$>3 \times ULN$

AND

- no other cause for the combination of the above laboratory abnormalities is apparent. Important alternative causes for elevated AST/ALT and TBL values include, but are not limited to:

- hepatobiliary tract disease
- viral hepatitis (eg, Hepatitis A/B/C/D/E, Epstein-Barr Virus, cytomegalovirus, Herpes Simplex Virus, Varicella, toxoplasmosis, and Parvovirus)
- right sided heart failure, hypotension, or any cause of hypoxia to the liver causing ischemia
- exposure to hepatotoxic agents/drugs or hepatotoxins, including herbal and dietary supplements, plants and mushrooms
- heritable disorders causing impaired glucuronidation (eg, Gilbert’s Syndrome, Crigler-Najjar syndrome) and drugs that inhibit bilirubin glucuronidation (eg, indinavir, atazanavir)
- alpha-one antitrypsin deficiency
- alcoholic hepatitis
- autoimmune hepatitis
- Wilson’s disease and hemochromatosis

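### Protocol 6.6, read literally, and the dose rationale in 4.3 leave room to resume study drug after a liver-related interruption that 7.4, the synopsis and the SAP summary treat as permanent

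*Protocol*

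**What the plan says.** Two sets of statements bear on what happens after study drug is interrupted for a liver problem.

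**No resumption**
- Protocol synopsis (1.1): "Hepatic related interruptions are permanent discontinuations". The technical summary at the front of the SAP repeats this under the test product.
- Protocol 7.4 forbids re-challenge once its hepatic criteria are met. It then extends the rule to an investigator's own decision to hold drug for abnormal values short of those criteria: "this is also considered a permanent discontinuation and the patient must not be re-challenged".

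**Resumption**
- Protocol 6.6, second paragraph, begins "Following a dose interruption for adverse events other than those related to renal labs". If the event may be drug-related, it says that "the investigator may restart the study drug when symptom(s) have resolved or have substantially improved", provided no safety concern remains. On dose it says "While investigators are encouraged to resume dosing at 2 tablets twice a day", with one tablet twice a day as an option. If the event recurs at the higher dose, it provides for a second interruption and, if drug is resumed, for one tablet twice a day.
- Protocol 4.3 has a sentence that begins "Since elevations in transaminases and declines in" eGFR by cystatin C and treats both as dose-related. It continues "by resuming drug at a lower dose for the remainder of the trial, the reoccurrence of the lab abnormality is expected" to be less likely. It refers to 6.6 for details of dose modification.

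**Linking text**
- Protocol 6.6, first paragraph: "For study drug dose management in relation to renal or hepatic abnormal laboratory values, see" 7.3 and 7.4.
- Protocol 7.1 treats an interruption as temporary at first, except where the protocol requires permanent discontinuation.

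**The concern.** The exception in 6.6 names one organ system and leaves out the other. The drug has both a renal and a hepatic signal, and the first paragraph of 6.6 mentions both. A reader who then finds only renal laboratory events excepted can conclude that hepatic events stay inside the restart rule. Section 4.3 supports that reading, because it names transaminase elevations when it explains why drug is resumed at a lower dose.

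At stake is a patient-safety instruction. Protocol 2.3.1 reports transaminase elevations in CY 5022 as dose dependent. For the same liver event, one reading permits re-exposure and the other takes the patient off drug for good. Exposure and discontinuation could then depend on which section a site opened, mostly in the arm where the events occur.

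**Working it through.** No stated figure depends on this point and no formula applies. The check is to take each kind of liver-related interruption through the sections.

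**Step 1. Does a hepatic laboratory hold count as an adverse event?** Protocol 8.3.1.1 includes clinically significant laboratory abnormalities that led to interruption of study drug. Protocol 7.4 makes clinically significant transaminase or bilirubin elevations adverse events of special interest. So one event can be both a laboratory value (7.4) and an adverse event (6.6, second paragraph).

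**Step 2. Three cases**

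| Case | 7.4 and synopsis | 6.6, second paragraph, read literally | In conflict? |
|---|---|---|---|
| A. Values meet a mandated stopping criterion in 7.4 | Permanent, no re-challenge | Restart permitted if the event is potentially drug-related | In wording only: the 6.6 pointer leads to 7.4, and 7.1 yields |
| B. Investigator holds drug for abnormal values below the mandated threshold, and the finding is clinically significant | Permanent, no re-challenge | Restart permitted if the event is potentially drug-related | Yes, softened by the pointer to 7.4 |
| C. Drug held for liver-related symptoms that are not handled as a laboratory value | Synopsis: permanent. The discretionary clause in 7.4 speaks of laboratory values | Restart permitted if potentially drug-related | Yes, and the pointer does not reach it |

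Case B is not remote. Under 7.4, an asymptomatic ALT or AST between 3 and 5 x ULN, with no bilirubin or INR criterion met, does not mandate a stop. Any hold there is at the investigator's discretion.

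Case C arises because 7.4 lists nausea, fatigue and rash among possible manifestations of liver toxicity. Such a hold may be recorded as a symptom event. (ALT or AST above 3 x ULN with symptoms consistent with hepatitis is a mandated stop and belongs in case A.)

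**Step 3. Does 4.3 settle it?** No. It describes resumption at a lower dose for renal and transaminase abnormalities alike. Section 7.3 provides that route for renal findings. Section 7.4 provides none for hepatic findings.

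**Step 4. How many patients?** Protocol 2.3.1 gives ALT or AST above 3 x ULN in 24 patients (7.0%) on reldesemtiv and 1 (0.9%) on placebo in CY 5022. These are elevations, not interruptions. Neither document gives a rate of discretionary hepatic holds or symptom-led liver interruptions, so the number in cases B and C cannot be derived.

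**The case against.** The best defence is that the operative text agrees with itself. Section 7.4, the synopsis and the SAP summary all point one way. Section 6.6 sends hepatic laboratory values to 7.4 before it states any restart rule. Its second paragraph is general, framed around symptoms, permissive, and conditional on there being no safety concern. A specific prohibition normally prevails over a general permission, and a site that does not restart complies with both. Section 4.3 is rationale and authorises nobody to restart. Temporary interruptions must be notified to the Medical Monitor (7.1), and clinically significant hepatic elevations must be reported within 24 hours (7.4).

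Much of this stands, and it narrows the point to cases B and C. It does not remove it: the exception still omits hepatic events, the pointer covers laboratory values only, and 4.3 describes the opposite of 7.4.

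Three stronger readings are tempting, and the documents do not support them.
- A reader might infer that 7.1 is also in conflict. It is not. It yields where permanent discontinuation is mandated, and it ties threshold-based resumption to the renal section only.
- A reader might apply the CY 5022 percentages to the planned arms to count affected patients. That would count elevations, not interruptions. The rates also pool all doses, including 450 mg twice a day, and come from 12 weeks of dosing, against 24 in the first period here. They are neither an estimate nor a firm ceiling.
- A reader might infer damage to the primary result. Protocol 7.2.1 encourages patients who stop drug to remain for outcome measures, and SAP Table 4 includes ALSFRS-R scores collected up to Week 24. No effect on the primary comparison has been shown.

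**Conclusion.** The contradiction is real and stands in current text. Followed literally, the restart paragraph in 6.6 permits what 7.4, the synopsis and the SAP summary forbid, and the transaminase wording in 4.3 does not fit 7.4.

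Its practical reach is limited mainly to discretionary holds for values below the mandated threshold and to liver-related events or symptoms not handled as laboratory values. Its size in patients is unknown. The CY 5022 rates (7.0% against 0.9%) support only the statement that the signal falls mostly on active drug.

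The conclusion rests on two readings: that a clinically significant laboratory abnormality leading to interruption is an adverse event, as 8.3.1.1 says, and that the exception in 6.6 means only what it names. That sites would in fact act differently is a risk, not something the documents show. The point still merits correction, because a re-challenge instruction should not depend on which section is read. It implies no view on which clinical rule is right.

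**What to change.** Reconcile the exception in the second paragraph of Protocol 6.6 and the transaminase wording in 4.3 with 7.4 and the synopsis, so that:
- a hepatic interruption, mandated or discretionary, has one stated outcome wherever it is mentioned;
- 6.6 says explicitly how hepatic adverse events are handled, including those first recorded as symptoms;
- the rationale in 4.3 describes the same handling as the operating sections.

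The SAP summary needs a change only if the synopsis sentence changes. Section 7.1 needs none on this account. The clinical rule is for the sponsor and its hepatology advisers to decide.

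The cost is wording in the next amendment and a letter to sites, with no new procedures, visits or patients.
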